14.2 Primary Objective

To assess safety and reactogenicity of administration of Pfs230D1-EPA/Matrix-M (all Arms):

- The frequency of systemic and local AEs will be summarized.
- A line listing of each clinical and laboratory AE classified as local, solicited, or other will be displayed in tables stratified by vaccine allocation.

- AEs will be summarized by severity and relationship to vaccine.
- The proportion of subjects with at least 1 AE will be compared by study group, and tests will be performed to assess whether these groups differ with respect to these proportions. To evaluate the difference in AEs between the initial vaccination and the subsequent vaccinations, a Wilcoxon signed-rank test (WSRT) will be performed, where the response for each subject is the difference between the numbers of AEs in the 7 days following each vaccination. To compare number and severity of AEs between control and vaccine arms, the Wilcoxon-Mann-Whitney test (WMW, also known as Wilcoxon rank sum test and Mann-Whitney U test) as well as linear regression may be used.
- SAEs occurring within the study period will be listed by relationship to vaccine.

14.3 Secondary Objectives

14.3.1 ELISA Analysis

There are several questions of interest related to antibody response, which include the change in ELISA values from baseline after a given number of doses of vaccine and the change in ELISA values between doses. To address these questions, we will use an arm-specific WSRT within the 20 subjects receiving a given vaccine dose.

The data from subjects who had Pfs230 ELISA measurements after receiving two doses on protocol #17-I-N006 (Pfs230/AS01 trial) allow us to estimate the SD of the log transformed Pfs230 ELISA responses at baseline (mean 3.688401 SD 0.5490291) and 3 months post vaccination 2 (mean 5.356736 SD 0.8868963).

Assuming similar values in this trial, there would be over 0.99 power to detect the difference between baseline and 3 months post vaccination 2. This approximate power is calculated counting the number of significant comparisons out of a thousand comparisons between random normal draws from N(3.68,0.55) and N(5.36, 0.88) using the Wilcoxon test.

Using the background information from protocol #17-I-N006, we have greater than 80% power to reject a 2-sided 0.05 level WMW test if the geometric mean Pfs230 ELISA baseline level was 2.3-fold higher geometric mean than the level of detection in the vaccinated group post vaccination 2. (Note: 2.3-fold is lower than the 5.31-fold observed in protocol #17-I-N006, so we treat these numbers as conservative.) This approximate power is calculated counting the number of significant comparisons out of a thousand comparisons between random normal draws from N(3.68,0.55) and N(3.68+log(2.3), 0.88) using the Wilcoxon test.

ELISA results will be analyzed by Wilcoxon-Mann-Whitney test, as the simulated power calculations were conducted.

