14.1 Sample Size

Safety:

The arms are sufficiently sized for safety. For each dose level (n=20) in Arms 1a combined with 2a, and 1b combined with 2b, 1c combined with 2c, and 1d combined with 2d, vaccination of 20 subjects gives a power of at least **0.80** for detecting 1 or more serious or severe AEs that occur with a probability of **0.077** or more per subject (or **0.90** for an event with a probability of **0.109**).

If we combine all treated groups (arms 1a/2a, 1b/2b, 1c/2c), with a total of 60 subjects, we have **80% power** to detect 1 or more serious or severe AEs that occur with a probability of **0.026** or more per subject (or **0.90** for an event with a probability of .037).

The aforementioned calculations do not assume any historical data; they are statistical consequences of the binomial distribution.

We will compare all AE event proportions between the control arm and treated arm by Fisher's exact test.

Immunogenicity:

We plan to do a test for an overall signal with a global analysis. That is, we will combine arms 1a/2a, 1b/2b, and 1c/2c into an "any vaccination" group of n=60 and combine arms 1d and 2d into a "control" group of n=20. Using historical data from the AS01 trial, we are well powered to detect a log difference (>99.9% power) and ½ log difference (99.7% power).

Following this global test, testing specific arms is of interest. To adjust for multiplicity, we use Bonferroni corrected alpha of 0.05/3. To investigate the specific arms we conduct three tests: arms 1a/2a vs controls, arms 1b/2b vs controls, and arms 1c/2c vs controls. The controls use arms 1d and 2d. This makes each analysis n=20 vs n=20. As such, we are well powered to detect a log difference (>99.9% power) and ½ log difference (89.2% power).

These calculations were made assuming normal distributions with mean and standard deviations from the AS01 trial. 1000 simulations were run to see how often a significant result came from a Wilcoxon-Mann-Whitney test (WMW).

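### Section 14.3.1 states its ELISA Wilcoxon-Mann-Whitney power at an unadjusted two-sided 0.05 and does not cite the 0.05/3 rule of 14.1, so the level for the arm-versus-control tests is left open to misreading

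*Combined protocol and SAP*

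**What the plan says.** Section 14.1 (Immunogenicity) plans a global comparison of all vaccinated participants (n=60) with controls (n=20). It then plans three tests: "arms 1a/2a vs controls, arms 1b/2b vs controls, and arms 1c/2c vs controls". On sample size it says "This makes each analysis n=20 vs n=20", and on the level "To adjust for multiplicity, we use Bonferroni corrected alpha of 0.05/3". Power there was simulated with the Wilcoxon-Mann-Whitney (WMW) test. Sidedness is not given.

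Section 14.3.1 (ELISA Analysis) assigns changes from baseline and between doses to a signed-rank test within each arm. It then makes a WMW power statement: "we have greater than 80% power to reject a 2-sided 0.05 level WMW test". The contrast is described as a baseline level and a "2.3-fold higher geometric mean than the level of detection in the vaccinated group post vaccination 2". The simulation used "random normal draws from N(3.68,0.55) and N(3.68+log(2.3), 0.88) using the Wilcoxon test". That statement gives no group size and names no control arm. The section closes with "ELISA results will be analyzed by Wilcoxon-Mann-Whitney test, as the simulated power calculations were conducted". It does not mention Bonferroni or refer back to 14.1.

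**The concern.** A statistician who opens the ELISA analysis section to find the level for the WMW tests finds only one, two-sided 0.05, followed by a line linking the analysis to the power simulations. Vaccine versus control is the only ELISA comparison that the plan explicitly assigns to WMW, and 14.1 puts its three arm-specific tests at 0.05/3. The stated power is therefore not power at the level those tests will use, and the section leaves room to apply 0.05 to them.

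What is at stake is the multiplicity control that 14.1 promises, and the reading of a weaker arm. The 20 µg arm was included to explore antigen dose-sparing (1.2), and the 12.5 µg arm also carries half the adjuvant (1.2.1). A borderline p-value is most plausible in such arms. The level should not be open to choice after unblinding.

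**Working it through.** **Inputs.** From 14.3.1: distributions N(3.68, SD 0.55) and N(3.68 + log 2.3, SD 0.88). From 14.1: 20 versus 20, and level 0.05/3 = 0.0167. Using n=20 for the 14.3.1 statement is an assumption, because that statement gives no n.

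**Log base.** The means in 14.3.1 differ by 5.356736 − 3.688401 = 1.668335, and exp(1.668335) = 5.30, which matches the stated 5.31-fold. The log is therefore natural and the shift is ln 2.3 = 0.833. Reading it as log10 would give only 32% power.

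**The plan's own figure.** Two-sided WMW by simulation, 20 versus 20:

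| Level | Power at 2.3-fold |
|---|---|
| 0.05 | 92% |
| 0.05/3 | 81% (asymptotic p), 82-83% (exact p) |

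The plan's claim of more than 80% is reproduced at 0.05 and also holds at 0.05/3. At 0.05, about 80% power is already reached at roughly 2.0-fold (81%).

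**Do the figures identify the level?** No. At 20 per group, 0.05/3 lies closest to 80%. But 15 per group, the size of a Main Group vaccine arm, gives 81% at 0.05. The 89.2% for a half-log difference in 14.1 cannot be checked either, because its SDs are not given. Taking half a log as ln 10/2 = 1.151 at 0.05/3, SDs of 0.55 and 0.88 give 98%, 0.887 in both groups gives 92%, and 0.92 in both gives 90%.

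**How often the level matters.** The share of arm p-values from 0.0167 up to 0.05 is the power at 0.05 minus the power at 0.05/3. At 2.3-fold that is about 92% − 81% = 11% (9-11% across runs). At the AS01-trial effect it is about 0.01% or less.

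**Family-wise error with no true effect, three tests.**
- At 0.05 each: the bound is 3 × 0.05 = 0.15, and independence would give 1 − 0.95³ = 14.3%. Simulation with the shared control gives 12.1-12.6%.
- At 0.05/3 each: the bound is 3 × 0.0167 = 0.05. Simulation gives 3.7-3.9%.
- At 0.05 each, but only after a significant global test at 0.05: 4.4-4.6%.

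**Holm instead of Bonferroni.** Holm compares the smallest p-value with 0.05/3, the next with 0.05/2 and the largest with 0.05, stopping at the first failure. With 2.3-fold in all three arms, average per-arm power is 89.5%, against 81.4% for fixed Bonferroni.

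**The case against.** A reader might infer that 14.3.1 sets the 20 versus 20 arm-versus-control test at 0.05, so that the same arm is positive under one section and negative under the other. The documents do not support that. The 0.05 sits in a power statement about baseline and post-vaccination-2 levels, with no n and no control arm. The first simulation in 14.3.1 also treats a baseline contrast as independent draws, so the name of the test does not identify the comparison. The closing line most naturally concerns the choice of test: 14.3.2 ends on the same formula and states no level at all. Nothing in 14.3.1 withdraws the explicit rule in 14.1.

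A reader might also infer that the power figure rules out 0.05. It does not: 92% is more than 80%, and the n behind the statement is unknown.

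The consequences are also conditional. Section 14.1 places the global test first, though it does not say that this test gates the arm tests. If it does, error under the complete null stays below 5% even at 0.05 per arm, although such a gate gives no general guarantee when some arms work and others do not. The 2.3-fold case is one that the plan itself treats as conservative.

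All of this stands. What remains is that the ELISA section gives one WMW level, unadjusted, with no reference to the adjusted one.

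**Conclusion.** The concern holds as an ambiguity and not as two rival decision rules. Section 14.1 gives the only explicit level for the arm-versus-control tests. Section 14.3.1 quotes power at a different, unadjusted level and permits a 0.05 reading without stating it.

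The family-wise error of about 12% instead of about 4% assumes that every arm is tested at 0.05, with no gate from the global test and no true effect. The figure of about 10% of p-values in the disputed range assumes a 2.3-fold effect, 20 versus 20 and the plan's own distributions; at 5.31-fold it is practically nil. Neither the sample size nor the claim of more than 80% power is affected. The endpoint is secondary in a phase 1 trial whose primary endpoint is safety, so this is a wording correction, worth making before unblinding.

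**What to change.** In 14.3.1, state that the arm-versus-control WMW tests are two-sided at the multiplicity-adjusted level of 14.1. Restate the 2.3-fold power as about 81-83% at 0.05/3, assuming 20 versus 20. Add the word two-sided to the rule in 14.1. In the same edit, give the level of the global test and of the within-arm signed-rank tests, and say whether the global test gates the arm tests.

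Preferably, replace fixed Bonferroni with Holm at overall two-sided 0.05. It keeps the same family-wise bound, rejects whenever Bonferroni does, and raises average per-arm power at 2.3-fold in all arms from about 81% to about 90%. This is an improvement and is not needed to remove the ambiguity.

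The cost is a few sentences. An arm p-value between 0.0167 and 0.05 could no longer be claimed on its own; under Holm it would count only if the step-down rule reached it. Simultaneous confidence intervals are less simple under Holm. No participants or assays are added.

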14.3.2 SMFA Analysis

For a group of 20 participants for each vaccine dosage, we anticipate about 90% power to detect a difference in TRAs of 32% (the observed difference in protocol #17-I-N006) and 80% power for a 40% difference. These power calculations come from a simulation assuming values similar to the SMFA data from protocol #17-I-N006, where the control group had an average TRA of 38 (SD 39) and a treatment group with SD 34. Thus, counting the number of significant comparisons out of a thousand comparisons between random normal draws from N(38,39) and N(38+40, 34) using the Wilcoxon test can give approximate power.

If TBAs are used, we will standardize the TBAs to a common target control mean first using previously established methods (Swihart, Fay et al. 2018). A nice feature of the standardized TBA is that its power is identical to those of the TRA.

SMFA results will be analyzed by Wilcoxon-Mann-Whitney test, as the simulated power calculations were conducted.

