pain, which was observed in about half of Pfs230D1M vaccinees. Of the related Grade 2 AEs, injection site pain was most common (7/11, 63%) followed by headache, fatigue, and injection site movement impairment in one subject. There were no related Grade 3 AEs. Participants in the Pfs230D1M booster arm experienced significantly more Grade 1 injection site pain and headache than the comparator arm. Grade 2 injection site pain was also reported more frequently in the Pfs230D1M arm but was not significantly different from the comparator.

[figure not shown]
3.2.2 Immunogenicity and Functional Activity (SMFA) of Pfs230D1M-EPA/AS01 in Healthy Adults (Primary Series + 4th Dose; Year 1 + 2)

Vaccination induced detectable antibody titers 2 weeks after the first dose, which increased further after dose 2, but the peak after a third dose was not significantly higher (Figure 11). There were no differences in titers between the low and high vaccine doses. Antibody function was assessed 2 weeks and 12 weeks after dose 2 (Figure 12). Anti-Pfs230 was sufficient to induce 100% TRA 2 weeks post dose 2, which was still >90% 12 weeks post dose 2. In contrast, anti-Pfs25 did not exceed 80% TRA post dose 2. The combination of Pfs25 and Pfs230 was not superior to Pfs230 alone for inducing functional serum activity.

Figure 11. Antibody Responses to Pfs230D1M-EPA/AS01 after Low Dose and High Dose Vaccinations of Adults in Sotuba, Mali during Pilot Phase trial.

[figure not shown]
A Low Dose Groups

B High Dose Groups

Response assessed by enzyme-linked immunosorbent assay (ELISA). (A) shows antibody responses of Malian adults after administration of low-dose vaccinations of Pfs230D1M-EPA/AS01 (either 13 μg Pfs230D1M alone or 16 μg Pfs230D1M-EPA/AS01 plus Pfs25M) at various time points out to 6 months. (B) shows antibody responses after administration of high-dose vaccinations of Pfs230D1M-EPA/AS01 (either 40 μg Pfs230D1M alone or 47 μg Pfs230D1M-EPA/AS01 plus Pfs25M) at various timepoints out to 6 months. Red arrows indicate immunization administrations at 0, 1, and 6 months. Dotted lines represent antibody titers to Alhydrogel-adjuvanted Pfs230D1M-EPA obtained in previous studies.

Figure 12. Antibody Function by Standard Membrane Feeding Assay to Pfs230D1M-EPA/AS01 after Low-Dose and High-Dose Vaccinations of Adults in Sotuba, Mali during Pilot Phase trial.

[figure not shown]

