- Use of chronic (≥14 days) oral or intravenous (IV) corticosteroids (excluding topical or nasal) at immunosuppressive doses (i.e., prednisone >10 mg/day) or immunosuppressive drugs within 30 days of Study Day 0.
- Allergy to latex or neomycin.

12. Receipt of:

- Live vaccine within 4 weeks prior to enrollment or a killed vaccine within 2 weeks prior to enrollment.
- Immunoglobulins and/or blood products within the past 6 months.
- Investigational malaria vaccine in the last 2 years.
- 13. Any other condition that in the opinion of the investigator would jeopardize the safety or rights of a subject participating in the trial, interfere with the evaluation of the study objectives, or would render the subject unable to comply with the protocol.

Co-enrollment guidelines: Co-enrollment in other trials is limited. Consideration for co-enrollment in trials evaluating the use of a licensed medication will require the approval of the PI. Study staff should be notified of co-enrollment on any other protocol as it may require the approval of the investigator. Enrolled subjects will be informed that they may be invited to participate in other subsequent studies.

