9.5.3 Standard Membrane Feeding Assays

Membrane-feeding assays demonstrate biologic activity of TBA and are critical to selection of vaccine candidates. SMFAs will be performed on sera obtained at baseline and periodically after vaccination as outlined in Appendix A. In a SMFA, test serum obtained from immunized subjects is mixed with parasites from a laboratory culture and the mixture is placed in a feeding cup covered with an artificial membrane. Pre-starved mosquitoes from a laboratory colony are allowed to feed through the membrane. A similar procedure is carried out on a malaria-naïve control serum at the same time using mosquitoes raised from the same laboratory colony. One week after the feed, mosquitoes are dissected, and midguts are stained with mercurochrome for the oocyst form of the parasite. The reduction of the proportion of oocyst-laden mosquitoes or the reduction of average oocyst numbers per mosquito compared to mosquitoes fed on the control group demonstrate biologic function of the antibody, and may be predictive of efficacy in the field. SMFA results have been shown to correlate with ELISA antibody titers against Pfs25 in several species (Cheru, Wu et al. 2010). The SMFAs will be conducted at LMIV and LMVR in Rockville, Maryland using laboratory-strain mosquitoes and parasites. Assays will compare feedings with the following:

• Plasma/sera.

• IgGs purified from the selected plasma/sera, mixed with a malaria-naïve human sera pool (to eliminate non-specific factors which may be present in plasma).

To confirm anti-Pfs230-specific TBAs, SMFAs may also be conducted by the following methods:

- Using Pfs230-specific IgG purified using affinity chromatography.
- Using test plasma/sera that has been depleted of Pfs230-specific antibodies using recombinant Pfs230 proteins.

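### The between-arm SMFA and ELISA tests make no use of the baseline samples the trial collects: valid, but a possible loss of efficiency, mainly in the per-dose SMFA comparison

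*Combined protocol and SAP*

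**What the plan says.** Section 14.3.2: "SMFA results will be analyzed by Wilcoxon-Mann-Whitney test, as the simulated power calculations were conducted". Section 14.3.1: "ELISA results will be analyzed by Wilcoxon-Mann-Whitney test, as the simulated power calculations were conducted". The simulations these sentences point to take one independent normal draw per participant. They contain no baseline term and no stratum.

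Section 14.1 compares each dose level with control, 20 vs 20, after combining pilot and main arms. For the comparator, "The controls use arms 1d and 2d". No stratification is mentioned.

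Baseline data will exist. Section 9.5.3 states that "SMFAs will be performed on sera obtained at baseline and periodically after vaccination", and Appendix A schedules ELISA and SMFA blood on Day -7 and on Day 1 before the injection.

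Baseline enters the planned analysis in one place only, the within-arm ELISA questions of Section 14.3.1 (change from baseline, change between doses): "To address these questions, we will use an arm-specific WSRT within the 20 subjects receiving a given vaccine dose". SMFA has no counterpart. Section 14.4.1 refers in general terms to standard methods and names no covariate.

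**The concern.** Section 1.1 says that malaria-exposed populations acquire antibody to Pfs230, and Section 3.1.2 reports that a few Malian adults in an earlier trial had responses before vaccination. If a participant's baseline predicts the later value, an unadjusted comparison leaves that predictable part in the error term. The trial pays for two baseline samples per participant, and the vaccine-versus-control test uses neither. The within-arm signed-rank test cannot replace it, because it does not compare vaccine with control.

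Power on the per-dose SMFA comparison is at stake. If adjustment is not specified in advance, it also becomes a choice made after the data are seen.

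**Working it through.** **Inputs.** From Section 14.3.2: control TRA mean 38, SD 39; vaccine SD 34; 20 per group; differences of 32 and 40 points. From Section 14.1: arm-specific alpha 0.05/3. That section does not say whether this alpha covers SMFA, so both levels are shown. Two-sided testing is stated for ELISA and assumed for SMFA. The baseline-to-outcome correlation ρ is in neither section and is varied by assumption.

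**1. The plan's own SMFA figures.** The pooled SD is √((39² + 34²)/2) = 36.6. The standard error is 36.6 × √(2/20) = 11.6. For 32 points, 32/11.6 = 2.77, and the normal approximation gives Φ(2.77 − 1.96) = 79%. Simulating the WMW itself from the plan's distributions gives:

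| Difference | Stated | WMW, alpha 0.05 | WMW, alpha 0.05/3 |
|---|---|---|---|
| 32 points | about 90% | 74-75% | about 56% |
| 40 points | 80% | 90-91% | 78% |

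The stated pair is not reproduced. It cannot hold for one design, because power falls as the difference grows. That is a separate error in the same section. The starting point used here is 74-75%.

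**2. Adjustment with the same ρ in both arms.** Adjustment multiplies the residual SD by √(1 − ρ²). Simulated power at 32 points, 20 vs 20 (4,000 replicates, simulation error about 0.7 of a point):

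| ρ | √(1 − ρ²) | Rank ANCOVA, 0.05 | Linear ANCOVA, 0.05 | Rank ANCOVA, 0.05/3 |
|---|---|---|---|---|
| 0 | 1.00 | 74% | 76% | 59% |
| 0.3 | 0.95 | 76-78% | 79% | 61% |
| 0.5 | 0.87 | 84% | 86-88% | 70% |
| 0.7 | 0.71 | 94% | 96% | 85% |

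At ρ = 0 linear ANCOVA is already slightly ahead of the WMW, because the simulated data are normal. That part is not a gain from baseline. TRA cannot exceed 100, so the rank-based column is the fairer guide.

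**3. Correlation in controls only.** If vaccination overrides the baseline, ρ is near zero in vaccinees. With control ρ of 0.3 to 0.7, vaccinee ρ of 0 and an assumed baseline SD of 39, rank ANCOVA gives about 75-79% at alpha 0.05.

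**4. Pilot/main stratum.** In each per-dose test, 5 of 20 vaccinees and 4 of 20 controls come from the pilot, so the shares are nearly equal. With no group difference, WMW gives 75% and the van Elteren test 74%. With an assumed 20-point TRA difference between pilot and main, the figures are 70% and 73%.

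**5. Where power is already adequate.** SMFA at 32 points with all vaccinees pooled, 60 vs 20, alpha 0.05: 89-90%. ELISA at a 2.3-fold difference, 20 vs 20: 92% at alpha 0.05 and 81% at 0.05/3, in line with the plan's statement of more than 80%.

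**6. Change scores are not the remedy.** With baseline SD assumed 39, a simple change score at 32 points and alpha 0.05 has 43%, 57% and 71% power at ρ of 0, 0.3 and 0.5. All are below the unadjusted WMW.

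**The case against.** The WMW is valid under randomisation, and its type I error already allows for chance baseline imbalance. These are secondary endpoints in a Phase 1 safety trial, and the stated test matches the simulation used to size it. All of this stands, so the point concerns efficiency and pre-specification only.

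The gain may also be small. Section 3.2.2 reports 100% TRA two weeks after dose 2 in the earlier AS01 pilot, and baseline cannot predict an outcome at its ceiling. This stands too, and is why the controls-only range is given beside the common-ρ range.

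A reader might infer more in four places:

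- **That control TRA of 38 (SD 39) proves natural Pfs230 immunity.** Section 14.3.2 does not attribute it. Section 9.5.3 allows for non-specific factors in plasma, and the SD also contains assay noise. Section 3.1.2 speaks of only a few pre-existing responders.
- **That the tests are stated to use post-vaccination values alone.** This is inferred from the simulation model and the absence of any baseline term. The text does not say it outright.
- **That ELISA is underpowered, or that baseline is ignored for it altogether.** Step 5 shows the first is wrong. The within-arm signed-rank test shows the second is wrong.
- **That eligibility adds avoidable prior immunity.** The exclusion reads "Investigational malaria vaccine in the last 2 years", and the captions to Figures 11 and 12 place the earlier AS01 pilot in Sotuba. But the documents do not say how many earlier recipients might volunteer, no effect can be quantified, and Exclusion 13 leaves the investigator discretion. This is a separate eligibility question and no part of this point.

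**Conclusion.** The point holds as an avoidable, possibly modest loss of efficiency. No between-arm ELISA or SMFA test uses the collected baseline or the pilot/main grouping, and nothing else in the plan supplies the adjustment.

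The consequence is mainly for per-dose SMFA at the 32-point difference seen in the earlier trial, where WMW power is about 74% (about 56% if 0.05/3 applies). At alpha 0.05, rank-based adjustment could raise this by a few points at ρ = 0.3, about 10 at 0.5 and about 20 at 0.7. If only controls show the correlation, power reaches at most about 79%. At ρ = 0 the cost is negligible. These figures rest on the plan's normal model and on assumed correlations, so the size of the gain is uncertain. The pilot/main term adds little unless the two groups differ substantially.

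**What to change.** Before unblinding, pre-specify a baseline-adjusted analysis for the between-arm tests:

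- ELISA: ANCOVA of the log value on arm, baseline and a pilot/main term.
- SMFA: rank-based ANCOVA of TRA with the same terms. Fix the rank form in advance and do not let it depend on inspection of residuals.
- Baseline: the mean of the Day -7 and Day 1 values. Do not use a raw change score.
- Supporting analysis: keep the WMW, stratified by pilot/main group (van Elteren).

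State the outcome time point in the same paragraph, since Section 14.3 does not name one for the between-arm tests.

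The cost is SAP wording and a little more analysis. No additional samples, visits or participants are needed.
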